## 7.2. Study Procedures

### 7.2.1. Baseline Examination

For enrolled patients that have provided informed consent the following baseline information will be collected on CRFs after informed consent requirements have been satisfied and before the procedures are performed:

1. Demographics (Age and Gender)
2. Gestational Age at Birth (*for Neonates only*)
3. Height and Body Weight
4. Relevant Medical History
5. Physiological Condition (Stable/Unstable)
6. Urine pregnancy test, if applicable (females of childbearing potential)
7. Arm or Thigh Circumference (cm)
8. Appropriate Cuff Brand (Critikon® Soft-Cuf or Classic-Cuf) and Size
9. Baseline Non-Invasive Blood Pressure (NIBP), consisting of systolic blood pressure (SBP) and diastolic blood pressure (DBP)
10. Location of NIBP Measurement (Arm/Thigh) and measuring circumference
11. Mean Arterial Pressure (MAP)
12. Current medications
13. Pulse rate

### 7.2.2. Before the Procedure

For each patient, the following procedure-specific information will be recorded on CRFs:

1. Model and serial number for the DASH® 4000 (if applicable)
2. Model and serial number for CARESCAPE B650 (if applicable)
3. Model and serial number for the PSM or PDM acquisition module used
4. Catheter cross-section, length, and trade name
5. Trade name of pressure transducer
6. Site/artery used for IBP measurements
7. Monitor filter settings and recording settings, if applicable
8. Identification of the observer making the recordings (name and position)
9. Details of any special circumstances during measurement
10. Pulse rate at the start of device evaluations
11. Time and date of last manometer calibration

Three ECG sensors will be placed with leads on the left and right arm and left leg connected to the DASH® 4000 or the PDM Data Collection Module

Before each patient procedure, static calibration will be conducted for the IPB system to ensure measurement accuracy according to the “Static Calibration” section of the *Device Set-Up*

*Manual* provided by the Sponsor. Each system will be calibrated at 5 static pressures spread across the working range of the device to be tested, recorded as:

1. Pressure for each of the 5 calibration static pressures tested
2. Calibration completion status (success/fail)
3. Descriptions of any errors during any static calibration procedure

### 7.2.3. Patient Procedures

Each patient will undergo intra-arterial aortic catheterization according to the standard of care at the investigational site. All tubing, transducers, and stopcocks will be filled with fluid and purged of all bubbles prior to data recording for IBP or NIBP in this study. If general anesthesia and/or other medicinal products are prescribed outside of the study, they will be administered according to the local standard of care prior to study measurements.

Dynamic calibration will be performed in the beginning of each procedure according to the "Dynamic Calibration" section of the *Device Set-Up Manual* provided by the Sponsor. For patients that the procedure will extended beyond one day, dynamic calibration will be conducted once each day prior to determinations. A maximum of 1 flush is to be conducted for patients aged <29 days. A maximum of 4 flushes may be conducted for patients aged  $\geq$ 29 days. During calibration, values will be recorded for:

1. Number of fast flushes
2. Damping coefficient
3. Natural frequency

For subjects less than 29 days of age, care will be taken to minimize disruption of care, and, when possible, procedures will be performed during times when feeding or other care is provided.

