### 2.3.1. Risk Analysis for Subjects with Indwelling Lines (≤29 days of age)

Eligible subjects aged 29 days or less will be recruited only if they currently have, or are scheduled to have, an indwelling femoral, radial, or umbilical arterial monitoring line placed. The type of line places will be determined according to the site standard of care, and not altered based on participation in the study. While radial lines are the most commonly placed indwelling lines in neonates, femoral and umbilical lines share a similar safety profile and, in some cases, are preferred in order to preserve integrity of vessels when future interventions may be required. Like radial and femoral line placements, umbilical lines have been shown to have a minimal complication rate even during longer procedures when performed by experienced physicians. For these subjects, NIBP measurements will be taken in a minimally disruptive manner in order to minimize possible interruption in their care. No additional lines will be placed for study purposes. These patients may participate for up to three days, taking as few determinations as necessary to accomplish research objectives each day under the supervision of a medically qualified investigator. There is not expected to be a significant risk to subjects based on placement of measurement devices in this study.

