### **2.3.2. Risk Analysis for Subjects undergoing Non-Emergent Aortic Catheterization (aged >29 days to adult)**

Patients aged 29 days or older having prescribed non-emergent aortic catheterization procedures will be enrolled. Typical catheterization procedures in pediatric patients involve the use of general anesthesia for the duration of the clinically indicated procedure. The risks associated with general anesthesia are well documented and are widely considered safe when prudently administered. Due to study participation, the duration of general anesthesia may be slightly increased by a period of about 25 minutes (1-2 minutes for each study NIBP measurement), after which no further research procedures will be performed. General anesthesia is widely recognized as a neuromodulator with potential neurotoxic effects; however, it is widely believed that prudent use of general anesthesia in pediatric patients does not pose significant acute or chronic risks to patients at routine clinical dosages and non-repeating administrations. As used in this study, the devices and study procedures are not expected to pose significant risks to participating subjects beyond those of their clinically indicated catheterization procedure.

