### 6.2. Protection of Vulnerable Subjects

The information collected in this study could not have been obtained in a less vulnerable, consenting population, necessitating the use of minor patients. Adolescent, pediatric, and neonatal patients will be recruited and enrolled according to all US FDA, ISO 14155:2011 GCP, and other applicable local requirements for protection of vulnerable subjects. Special measures will be taken to protect the rights of these vulnerable study participants and to shield them from undue risk. Study procedures for pediatric and neonate subjects will be modified to minimize interruption in normal medical care, which includes additional limitations on sampling frequency beyond the minimums suggested by ISO 81060-2:2013 (as shown in Table 2) for the general population. This is done to ensure minimal risk for participating subjects.

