## 6.4. Inclusion Criteria

Subjects will be included that:

1. Are aged >29 days requiring clinically indicated non-emergent heart catheterization OR aged ≤29 days with placed or scheduled placement of an indwelling femoral, radial, or umbilical arterial monitoring line;
2. Have an upper limb (right OR left side) that fits a cuff size of the device (circumference ranging 3 cm to 40 cm) OR have a thigh (right OR left side) that fits a cuff size of the device (circumference ranging 38 to 50 cm);
3. Are expected to be able to provide blood pressure measurements using both IBP and NIBP;
4. Are able and willing to provide written informed consent or have a legally authorized representative willing to provide written informed consent with assent from minor patients, as required by IRB policy.

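### An infant aged exactly 29 days is enrolled with the neonates but gets the older-patient flush maximum and no Table 2 interval or target; 9.3 and Table 1 hold two smaller age-band mismatches

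*Combined protocol and SAP*

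**What the plan says.** Enrolment uses a cut that includes day 29 on the young side. Inclusion criterion 1 (6.4) admits those "aged ≤29 days with placed or scheduled placement of an indwelling femoral, radial, or umbilical arterial monitoring line", and sends only those older than 29 days to the catheterization route. Section 2.3.1 agrees: "Eligible subjects aged 29 days or less will be recruited only if they currently have, or are scheduled to have" such a line. It adds: "These patients may participate for up to three days".

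The procedures use other cuts. In 7.2.3, "A maximum of 1 flush is to be conducted for patients aged <29 days", while "A maximum of 4 flushes may be conducted for patients aged" 29 days or more. The same section says "For subjects less than 29 days of age, care will be taken to minimize disruption of care", which stops short of day 29. Table 2 has one row for neonates under 29 days and one for infants over 29 days. The flush example in exclusion criterion 6 also names only those two groups. Section 2.3.2 is headed for patients over 29 days, yet its text reads "Patients aged 29 days or older having prescribed non-emergent aortic catheterization procedures will be enrolled".

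Two further bands do not match. The over-5-kg bullet in 9.3 lists 29 days to under 1 year and 2 to under 3 years, whereas the Table 1 PSM stratum runs from 1 to under 3 years. Table 1 has pediatrics under 12 and adults/adolescents over 12, whereas 9.3 closes the pediatric band at 12 inclusive.

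**The concern.** The flush limit and the Table 2 spacing are safeguards for the youngest patients, and 6.2 names Table 2 as the place where the extra sampling limits are held. A safeguard should use the same age cut as the rule that puts the infant on the line route. At 29 days it does not: the flush ceiling is the older-patient one, and the spacing and target are not assigned at all. Because line-route infants may take part over several days, a site also needs to know whether age at enrolment or age on the day governs, and no section says.

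The other two mismatches concern counting. One descriptive tally leaves out children whom the plan enrols and analyses. One age has no quota cell.

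**Working it through.** The plan states no figure that can be reproduced here, so the check applies each stated age rule at the boundary.

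**(a) Day 29**

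| Rule | Stated cut (days) | Age 28 | Age 29 | Age 30 |
|---|---|---|---|---|
| 6.4, criterion 1 | ≤29 / >29 | line | line | catheterization |
| 7.2.3 flush maximum | <29 / ≥29 | 1 | 4 | 4 |
| Exclusion 6 flush example | <29 / >29 | 1 | not named | 4 |
| Table 2 row | <29 / >29 | neonates | none | children and infants |
| 9.3 age bullet | <29 / ≥29 | younger | older | older |

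No other section supplies the missing interval. In 7.2.4 the wait between readings is taken from Table 2. The 3-minute wait there is step 2, and only steps 3 and 4 are repeated.

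Minimum waiting time under each neighbouring row of Table 2:
- Neonatal row, 3 minutes, target 5-10: 4 gaps × 3 = 12 minutes for 5 readings, up to 9 gaps × 3 = 27 minutes for 10.
- Older-infant row, 60 seconds, target 10: 9 gaps × 1 = 9 minutes.
- Both rows cap attempts at 10.

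Who is affected depends on which age governs:
- Age at enrolment: entry at 29 days only.
- Age on the day: Table 2 allows 72 hours, which is 3 days. Entry at 25 gives 25 + 3 = 28, not affected. Entry at 26 gives 26 + 3 = 29, affected. So entry at 26, 27, 28 or 29 days can be affected.

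**(b) Over-5-kg bullet in 9.3**

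The PSM minimum under 3 years is 3 + 3 + 3 = 9 (Table 1). Children aged 1 to under 2 years can fill the 1-to-under-3 row (3) and the no-age row (3). At minimum enrolment the bullet read alone can therefore miss 0 to 6 of the 9. However, every PSM patient must weigh over 5 kg (Table 1, footnote a), and the preceding 9.3 bullet already counts 1 to under 3 years by arm. In that arm the count is available anyway.

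**(c) Age 12**

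Table 1 has five rows for patients aged 3 or more: adult female, adult male, atrial fibrillation, pediatric female and pediatric male. Age 12 meets 0 of the 5. Section 7.2.1 does not say how age is recorded. In completed years the gap covers the whole year of being 12; in fractional years it covers only exactly 12.0.

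**The case against.** The strongest reply is that little turns on this.

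- Section 2.3.1 covers everyone up to and including 29 days. It gives them the three days, asks for readings with little disturbance and as few as the research needs, and requires a medically qualified investigator. A reader might infer from 7.2.3 and Table 2 that a 29-day-old has no multi-day allowance and no protection from disruption; 2.3.1 shows otherwise. This stands.
- The limits are permissive. One flush, 3-minute gaps and 10 readings satisfy 7.2.3 and both neighbouring Table 2 rows, so nothing forces a breach. This stands.
- A reader might infer that 1 flush was intended on day 29. The documents do not show it: 7.2.3, the text of 2.3.2 and the 9.3 bullets all place day 29 with older infants. The mismatch with 6.4 is a fact; which side should move is a judgement. Flush technique is also delegated to a set-up manual that is not among the documents.
- On (b), Appendix B records that the 1-to-under-2 band was struck from this bullet, so its absence may have been deliberate. The current bullet still does not match the current Table 1 stratum or the 9.1.1 population.
- On (c), 5.2 lets patients be enrolled without a quota cell once quotas are met, and 9.1.1 analyses everyone aged 3 or more. This stands.

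The boundary conflict remains after these points. A site cannot tell from the text which Table 2 row applies at 29 days.

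**Conclusion.** The inconsistency is real and minor. For an infant aged exactly 29 days on the line route, the flush ceiling is 4 rather than the 1 allowed to younger line-route infants, and Table 2 fixes neither interval nor target. This is a small loosening of a safeguard. It reaches one day of age, or entry at 26 to 29 days if age on the day governs, which is an assumption because the plan is silent.

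Other stronger readings are not supported. The infant is not ineligible and does not lack a quota cell: the no-age rows of Table 1 can take this child, and the general clause of exclusion 6 still applies. Multiplying the flush ceiling over several daily calibrations would assume that it applies to each calibration, which 7.2.3 does not say. Part (b) touches one descriptive count. In part (c) a 12-year-old fills no stratum as written, but is not lost from the analysis.

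The accuracy analyses split at 3 years, so they do not move. The arm minimums (45 and 29) and the pass/fail rule are also unchanged.

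**What to change.** 1. Use ≤29 days at enrolment and >29 days at enrolment in 2.3.2, exclusion criterion 6, 7.2.3 (both flush limits and the disruption sentence), Table 2 and the 9.3 age bullets. This follows the cut already in 6.4, 2.3.1 and the Table 1 infant stratum. It keeps line-route infants on the 1-flush limit, the 3-minute interval and the 5-10 target throughout, and settles which age governs.
2. In the over-5-kg bullet of 9.3, change the upper band from 2-to-under-3 years to 1-to-under-3 years.
3. In Table 1, set pediatrics to at least 3 and at most 12 years, which fits 9.3 and the existing over-12 stratum.

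The cost is wording in six places (2.3.2, Table 1, exclusion 6, 7.2.3, Table 2 and 9.3), with the ethics review and sponsor approval that 13.3 requires for any amendment. No new data are needed and no minimum changes in size; a 12-year-old simply gains a stratum to count toward.

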### 7.2.4. Blood Pressure Assessments

NIBP will be measured using the CARESCAPE Monitor B650 patient monitor equipped with an acquisition module (either PDM-SuperSTAT or PSM-Datex-Ohmeda, determined by study arm). IBP will be measured using the DASH® 4000 plus DC-COLLECTOR and DC-EDIT software. For PDM procedures where the PDM Data Collection Module is used for electronic data capture, this may be used in place of manual transcription from the patient monitor to paper CRFs. During the blood pressure assessments, values will be recorded for:

1. Study Arm
2. Time of first and last blood pressure measurement
3. Systolic, Diastolic, Mean, Test Duration
4. If the prescribed wait time was taken between tests
5. Any measurements with no determination

Both NIBP and IBP assessments will be conducted simultaneously, using either digital data recording tools (when available) or recorded by hand onto a paper Case Report Form (CRF). If

necessary, assistance will be provided by other study staff to ensure that accurate and simultaneous blood pressure data is recorded.

IBP data will be continuously collected throughout the study.

For cases where manual data collection of NIBP data is necessary, it will be recorded according to the following procedure:

1. Use the patient monitor equipped with either PDM-SuperSTAT or PSM-Datex-Ohmeda according to the patient's study arm to determine the patient's blood pressure.
2. Clear the patient monitor memory of the previous determination and wait at least 3 min
3. Have the observers using the reference IBP monitoring equipment (DASH® 4000) and the NIBP monitoring equipment (CARESCAPE Monitor B650 with either PSM or PDM) simultaneously record and determine the patient's blood pressure, as follows.
  - a. Start continuous collection on the IBP DCS system at the same time as recording of NIBP begins
  - b. Collect each NIBP measurement from the CARESCAPE Monitor B650
4. Wait the appropriate amount of time between determinations (as defined in [Table 2](#)).
5. Repeat steps 3 and 4 adhering to the requirements in [Table 2](#) until the target number of recordings and determinations have been performed or the subject leaves the study. In the event that any blood pressure determination is not successful, the procedure may be repeated to achieve the target number of successful blood pressure determinations. No more than the maximal number of total blood pressure determinations as specified in [Table 2](#) will be performed on any patient.
6. When all NIBP measurements are complete, stop the IBP data collection.

For PDM procedures where the PDM Data Collection Module is used, data may be captured electronically instead of using the manual procedure according to the following procedure:

1. Use the PDM Data Collection Module to determine the patient's blood pressure.
2. Wait at least 3 min.
3. Simultaneously record and determine the patient's blood pressure, as follows.
  - a. Start NIBP measurement from the PDM Data Collection Module
4. Wait the appropriate amount of time between determinations (as defined in [Table 2](#)).
5. Repeat steps 3 and 4 adhering to the requirements in [Table 2](#) until the target number of recordings and determinations have been performed or the subject leaves the study. In the event that any blood pressure determination is not successful, the procedure may be repeated to achieve the target number of successful blood pressure determinations. No more than the maximal number of total blood pressure determinations as specified in [Table 2](#) will be performed on any patient.
6. When all NIBP measurements are complete, stop the data collection.

The same number and type of determination should be performed whether the manual or digital PDM Data Collection Module is used.

**Table 2 – Number of Blood Pressure Assessments and Frequency**

Population	Maximum Number of BP Determinations	Target Number of Valid BP Determinations	Frequency of Determinations
Pediatric, Adolescents, and Adults (aged ≥ 3 years)	15 max attempts	10 determinations	At least 60 s between determinations
Children & Infants (<3 years old to >29 days old)	10 max attempts	10 determinations	At least 60 s between determinations
Neonates (< 29 days old)	10 max attempts	5-10 determinations	At least 3 minutes between determinations (over max of 72 hours)

### 7.3. Data Storage

All digitally recorded data will be saved from the DCS folder to a Sponsor-provided external media (e.g., flash drive or CD), and the Investigator will confirm that all data is saved on flash drive or CD and stored in a secured area at the investigational site. When NIBP data is recorded on paper case report forms, it will be stored in a secure area at the investigational sites.

### 7.4. Withdrawal and Discontinuation Criteria

The patient may withdraw from study participation at any time, for any reason without consequence. The Investigator may withdraw a patient at any time for any reason. The reasons for withdrawal and discontinuation for any patient shall be recorded. These will be reported to the Sponsor. The EC/IRB should be notified per their notification of patient withdrawal policy.

Data collected up until the time of withdrawal may still be disclosed to the Sponsor as part of this study to ensure the integrity of research data.

Continuation and discontinuation of enrollment in any stratification group will be made at the discretion of the Sponsor in the context of applicable regulatory and standards requirements, and the Investigator will be notified by the Sponsor upon such a determination.

## 8. TRAINING PLAN

### 8.1. Training Plan for Research Device/Product

All device evaluations will be conducted by trained observers that understand blood pressure measurement and have been recently trained in blood pressure measurement. Training for clinical investigators will be provided by the Sponsor to ensure that procedures are conducted in accordance with procedures outlined in this protocol. The current commercially available *GEHC*

CARESCAPE Monitor B650 User Manual, DASH® 4000 User Manual, and a Sponsor-provided Device Setup Manual for this study will be provided to the investigational site. The Sponsor may also provide additional training on these materials to ensure proper device usage.

## 8.2. Training Plan for Protocol

All investigators and study staff will be provided training on the protocol and procedures prior to study initiation. Any investigator or study staff may request additional training to ensure that study procedures are conducted in accordance with the protocol.

## 9. DATA ANALYSIS AND STATISTICS

### 9.1. Statistical Analysis Methods

#### 9.1.1. Analysis Populations

Separate analysis will be performed for PSM-Datex-Ohmeda and the PDM-SuperSTAT arms per requirements of the ISO 81060-2:2013 standard. Analyses will be conducted for the following populations:

- adults, adolescents, and pediatric patients, who are  $\geq 3$  years old and chronic atrial fibrillation patients (PDM-SuperSTAT arm)
- adults, adolescents and pediatric patients, who are  $\geq 3$  years old (PSM-Datex-Ohmeda arms)
- neonates and children  $< 3$  years of age (PDM-SuperSTAT arm)
- children  $< 3$  years of age and weigh over 5 kg (11 lbs) (PSM-Datex-Ohmeda arm)

If deemed necessary by the Sponsor, when the measurement accuracy is compromised in a sub-population, affected sub-populations may be excluded from analysis

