## 4. OBJECTIVES OF RESEARCH STUDY

### 4.1. Hypothesis

This is a study conducted to satisfy the ISO 81060-2:2013 standard for two NIBP devices (PSM-Datex-Ohmeda and PDM-SuperSTAT) and, as such, does not require a statistical hypothesis. The Pass/Fail criteria are described in **Section 9.5 - Pass/Fail Criteria**.

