## 4.2. Study Objectives

### 4.2.1. Primary Objective:

The primary objective of the study is to determine if the PSM-Datex-Ohmeda and PDM-SuperSTAT NIBP measurement devices provide accurate blood pressure measurements in all indicated patient populations (neonates, children, pediatrics, adolescents and adults, and special populations) according to the definitions set forth by ISO 81060-2:2013.

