## 4.3. Study Endpoints

### 4.3.1. Primary endpoints:

Per patient, NIBP and IBP endpoints will be collected for:

- Systolic BP (mmHg)
- Diastolic BP (mmHg)
- NIBP and IBP Mean Arterial Blood Pressure (MAP)

Per patient, for NIBP only:

- Accuracy, determined according to ISO 81060-2:2013

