### 6.3. Number of Subjects

The total minimum enrollment for the two study arms is 83 total evaluable patients (maximum of 200 patients), as follows:

1. **PDM-SuperSTAT Arm ( $N_{PDM}$ ):** 45 evaluable patients with GE DINAMAP® SuperSTAT algorithm (PDM Module) on CARESCAPE Monitor B650, to achieve a total target of  $\geq 150$  BP data pairs in patients  $\geq 3$  years old (up to 10 paired measurements per subject) and  $\geq 150$  BP data pairs in patients  $< 3$  years old (as described in Table 2).
2. **PSM-Datex-Ohmeda Arm ( $N_{PSM}$ ):** 29 evaluable patients with Datex-Ohmeda algorithm (PSM module) on CARESCAPE Monitor B650, to achieve a total of  $\geq 150$  BP data pairs in patients  $\geq 3$  years old (up to 10 paired measurements per subject) and  $\geq 150$  BP data pairs in patients  $< 3$  years old (as described in Table 2).

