#### 9.2.1. Analysis of Blood Pressure Measurement Error

The BP measurement error of the investigational device will be determined as follows:

- If the value obtained from the investigational device lies within the range of reference IBP, an error of 0 mmHg will be assigned to this determination.
- If the value obtained from the investigational device lies outside the range of the IBP, the error for this determination will be calculated by subtracting the

adjacent limit of the IBP range from the value of the NIBP determination ( $\Delta = \text{NIBP} - \text{IBP}$ ).

Then, mean and SD will be calculated from the errors of each determination of each patient using the following formulae, and will be compared to the acceptance criteria, i.e., mean  $\leq 5$  mmHg and SD  $\leq 8$  mmHg. Percentages of measurements with errors within 5 mmHg, 10 mmHg, and 15 mmHg will also be calculated.

Mean: 
$$\bar{x}_n = \frac{1}{n} \times \sum_{i=1}^n x_i$$

SD: 
$$s_n = \sqrt{\frac{1}{n-1} \times \sum_{i=1}^n (x_i - \bar{x}_n)^2}$$

In addition, Bland-Altman plot will be presented for the measurement agreement between NIBP and reference IBP. The ‘average’ (x-axis) represents the average of the blood pressure from the investigational device and the mean reference IBP value. The ‘difference’ (y-axis) is the blood pressure measurement difference calculated as  $\Delta = \text{NIBP} - \text{mean IBP}$ .

Population mean bias, between-subject variance, within-subject variance, and limits of agreement will be calculated for the measurement difference using Bland-Altman method as described in the article “Agreement Between Methods Of Measurement With Multiple Observations Per Individual” by Bland and Altman in 2007 Journal of Biopharmaceutical Statistics.

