## 9.4. Interim Analysis

No interim analysis is planned. As necessary for study conduct, engineering, and/or regulatory purposes, study data may be accessed and, if necessary, reported by the Sponsor prior to closure of the study.

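### The sponsor may drop a sub-population because accuracy is poor in it, so the primary accuracy result can be selected on its own outcome and a failing device can pass

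*Combined protocol and SAP*

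**What the plan says.** Section 9.1.1 defines four analysis populations, two per arm, split at 3 years of age. It then adds: "If deemed necessary by the Sponsor, when the measurement accuracy is compromised in a sub-population, affected sub-populations may be excluded from analysis".

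The related provisions are:

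- Section 4.2.1: the primary objective is to determine whether the devices "provide accurate blood pressure measurements in all indicated patient populations", and its list of these includes special populations.
- Section 4.3.1: the primary endpoint for NIBP is "Accuracy, determined according to ISO 81060-2:2013".
- Section 9.2.1: the mean and SD of the errors "will be compared to the acceptance criteria, i.e., mean $\leq 5$ mmHg and SD $\leq 8$ mmHg".
- Section 4.1: the study "does not require a statistical hypothesis", so these limits are the only numerical decision rule.
- Section 9.1.1, first population: patients aged 3 years or more are combined with AF patients ("years old and chronic atrial fibrillation patients (PDM-SuperSTAT arm").
- Section 9.4: "study data may be accessed and, if necessary, reported by the Sponsor prior to closure of the study".
- Section 9.6: the study passes if the data set collected is sufficient for the ISO standard. It does not say that every planned sub-population must remain in the analysis.

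**The concern.** The ground for exclusion is the same quantity as the primary endpoint. A group in which NIBP departs from the invasive reference may be removed, and the mean and SD are then calculated on what is left. The sponsor makes the decision and may have seen the data. The remaining result does not answer the stated objective, which is accuracy in all indicated populations.

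The risk is foreseeable. Section 2.1 itself says that the accuracy of these algorithms varies widely with age and cardiac disease status, which describes the groups most likely to be removed.

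AF is exposed in a second way. Its 7 patients are pooled with 20 others, and no section asks for their error separately: Sections 9.2.3 and 9.3 call for counts and characteristics only. A failure in AF would therefore be either diluted or excluded. A reader could not tell whether the device is accurate in AF, in the smallest neonates or in any other difficult group.

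**Working it through.** **Inputs from the documents.** Table 1 gives PDM minimums of 15 general adults and adolescents, 7 AF, 5 pediatric and 18 children, infants and neonates. The sum is 15 + 7 + 5 + 18 = 45, which reproduces the arm size in Section 6.3. Patients give up to 10 pairs each, and the target is at least 150 pairs in each age group (Section 6.3). The limits are mean 5 and SD 8 mmHg (Section 9.2.1).

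**Does the pair target prevent exclusion?** PDM patients aged 3 years or more number 15 + 7 + 5 = 27, giving up to 270 pairs. Without AF, 20 × 10 = 200 remain. Without AF and pediatrics, 15 × 10 = 150 remain. Both meet the target.

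**Assumed inputs.** The documents give no error means or SDs. The values below are assumptions about errors as scored under Section 9.2.1, after zero has been assigned to readings inside the reference range.

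**Formulas.** For groups of n_g pairs with mean m_g and SD s_g:

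- pooled mean M = Σ n_g m_g / N
- pooled SD = √{[Σ (n_g − 1) s_g² + Σ n_g (m_g − M)²] / (N − 1)}

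**Exclusion, worked case.** AF has 70 pairs, mean 10, SD 10. The others have 200 pairs, mean 2, SD 6.5.

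- M = (70 × 10 + 200 × 2) / 270 = 4.07
- Within-group sum of squares = 69 × 100 + 199 × 42.25 = 15,307.75
- Between-group sum of squares = (70 × 200 / 270) × 8² = 3,318.5
- SD = √(18,626.3 / 269) = 8.32, a fail. Without AF the result is 2 and 6.5, a pass.

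**Other assumed values (mean / SD, mmHg).**

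| Others | AF | Pooled | Pooled result | Without AF |
|---|---|---|---|---|
| 2 / 7 | 10 / 10 | 4.07 / 8.62 | fail | pass |
| 2 / 6 | 12 / 10 | 4.59 / 8.46 | fail | pass |
| 0 / 7 | 8 / 10 | 2.07 / 8.62 | fail | pass |
| 2 / 6 | 8 / 10 | 3.56 / 7.70 | pass | pass |
| 2 / 6 | 10 / 8 | 4.07 / 7.44 | pass | pass |

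**Youngest group.** The PDM arm has 18 patients under 3 years, up to 180 pairs. Take 30 pairs below 1000 g at 12 / 10 and 150 others at 3 / 7. The pooled mean is (360 + 450) / 180 = 4.5. The SD is √[(29 × 100 + 149 × 49 + 25 × 81) / 179] = 8.26, a fail. Without the lightest band the result is 3 / 7, a pass.

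**Simulation.** This used 20,000 runs, 10 pairs per patient, normal errors with a random patient effect, and a pass defined as absolute mean at most 5 and SD at most 8.

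- Others 2 / 7, AF 10 / 10, within-patient correlation 0.3 to 0.7: the chance of passing is 16–26% with AF kept and 91–98% with AF dropped.
- No true difference between groups, mean 0, correlation 0.5: at a true SD of 8.5 the chance of passing is 28% on the full population, 38% with the option to drop AF after seeing the data, and 49% with the option to drop AF, pediatrics or both. At a true SD of 9 the figures are 9%, 16% and 25%.

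**Dilution when AF is kept.** Let the others have mean 0, the common within-group SD be w, and p = 70/270. The AF bias d that brings the pooled SD to 8 is approximately d = √[(64 − w²) / (p(1 − p))], with p(1 − p) = 0.192.

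- w = 5: d = 14.3, pooled mean 3.7
- w = 6: d = 12.1, pooled mean 3.1
- w = 7: d = 8.8, pooled mean 2.3

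An AF bias of about 9 to 14 mmHg could thus sit inside a passing result.

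**The case against.** The strongest reply is that the clause may have been meant for technical faults. Section 7.2.2 uses the phrase measurement accuracy for calibration of the invasive system, while Section 9.2.1 calls the device result measurement error. That reading is possible, but nothing limits the sentence to it. Wide reference ranges and premature ventricular beats already have their own rules in Sections 9.2 and 9.3.1. Appendix B (item 33), where the sentence enters, justifies it only by the removal of another standard's requirements.

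A second reply is that Table 1 requires AF patients and each weight band, and that Section 9.6 refers to a standard that cannot be consulted here. Table 1 governs enrollment, and under Section 6.3.1 the sponsor decides which datasets are evaluable. No section says that an exclusion fails the arm or narrows the accuracy claim. It is fair that the change from fail to pass concerns the Section 9.2.1 limits, which Section 9.6 reaches only through the standard.

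Third, the magnitudes are assumed. This stands: milder AF error passes with or without exclusion, and nothing in the documents supports particular values. The example below 1000 g is also fragile, because 150 remaining pairs require all 15 remaining minimum patients to reach 10 pairs, while Table 2 caps them at 10 attempts and accepts 5 to 10 determinations in neonates.

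Fourth, a separate AF result is descriptive with 7 patients, and whether the standard calls for pooling cannot be checked. This also stands, but a descriptive row does not conflict with a pooled analysis. Open-label conduct matters less than the sponsor's access to the data, since the device readings are automated.

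**Conclusion.** The concern holds, and the sentence must be changed. As written, poor accuracy can be used at the sponsor's discretion to remove the group that shows it, and a device that fails the Section 9.2.1 limits on its full population can pass on the remainder. This defect is in the rule and does not depend on the errors eventually observed.

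Its numerical size does depend on them. Under the assumed values, removing AF moves the result from 4.07 / 8.32 to 2 / 6.5, and the simulated chance of passing rises from 16–26% to 91–98%. With no true group difference and a borderline device (SD 8.5), the option to choose after seeing the data adds 10 to 21 percentage points (28% to 38% or 49%). With milder AF error the verdict does not change, and the remaining problem is that AF accuracy is not visible.

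**What to change.** Delete the sentence in Section 9.1.1. In its place, state that every pair from every enrolled patient in the four populations enters the primary analysis whatever its error, except pairs removed under Sections 9.2 and 9.3.1 or missing under Section 9.5. Define *evaluable* in Section 6.3.1 without reference to the NIBP-minus-IBP error, so that the same discretion does not return by that route.

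If a technical exclusion at sub-population level is needed, list the reasons in advance, have them judged without sight of the errors, and report the result with the excluded data included.

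If a sub-population performs poorly, report the full-population result as primary, show the sub-population in its own row, and limit the accuracy claim accordingly. Beside the pooled PDM result for patients aged 3 years or more, add one row for chronic AF alone (patients, pairs, mean, SD) and one for PDM without AF.

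The cost is one sentence replaced, one definition and two table rows. The sponsor loses the option to rescue a failing population by exclusion. The AF row will be imprecise: with an assumed SD of 10 and within-patient correlation of 0.5, the standard error of its mean is 10 × √(0.5/7 + 0.5/70) = 2.8 mmHg. It should be presented as descriptive.
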